#### **10.3.4. Quality of life analysis**

The expectation is that changes in patient quality of life will not differ significantly between the two treatment groups. Changes in patient quality of life over time will be investigated with particular attention paid to the following characteristics: Physical function, cognitive function, and fatigue (EORTC-QLQ-C30), pain (BPI-SF) and urinary symptoms (EORTC-QLQ PR25).

Detailed hypotheses will be developed in the statistical analysis plan (SAP).

#### **10.3.5. Geriatric status**

Patient autonomy will be evaluated using ADL and 4-IADL evaluations. Change over time in ability to perform ADL and IADL will be investigated.

For exploratory purposes, Time to definitive deterioration in ADL will be compared. Time to definitive deterioration of ADL will be defined as the interval between randomisation and the first decline in the ADL score  $\geq 2$  points compared to the ADL at inclusion with no further improvement in score  $\geq 2$  points. Progression or death will be considered as an event.

In a complementary analysis, competing risks approach will be used to decompose Time to definitive deterioration of ADL considering death and progression as a competing event.

Change over time in other geriatric parameters will be investigated.

#### **10.3.6. Missing data**

For time-to-event endpoints, missing values will be handled thanks to censoring. For all other endpoints, valid percent (excluding missing values) will be reported in the descriptive tables; number of missing data will be reported for each parameter.

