#### STATISTICAL ANALYSIS:

For primary and secondary efficacy endpoints, the analysis will be performed on the ITT population, i.e. all randomised patients will be included, whether eligible or not, compliant or not. Patients will be analysed according to their randomisation arm, regardless of the actual treatment received.

Analysis of the primary endpoint will be event-driven. Time to event endpoints will be reported using the Kaplan-Meier method with Rothman's 95% confidence intervals. A log-rank test will provide the statistical significance of the randomised treatment effect. Additionally a Cox model will provide an estimate of the randomised treatment effect (hazard ratio).

Stratification factors will include: LATITUDE risk criteria (high risk versus low risk, [Fizazi, 2017](#)) and ECOG performance status score (0 or 1 vs. 2).

Qualitative data will be expressed as percentages and compared between the treatment groups using the chi-square test (or the Fisher exact test). Quantitative data will be expressed as means and standard deviation (or medians and range) and compared between the treatment groups using the Student t-test (or the Wilcoxon test).

The analysis of the secondary endpoints will be performed using a formal adjustment for multiple testing.

One interim analysis will be performed after observing at least 70% of the number of expected events (i.e. at least 138 events). Stopping rules using the spending function approach of Lan and DeMets with O'Brien-Fleming type spending function will be followed to conclude at each sequential analysis.

Nominal p values for overall type I error of 0.05 Lan-DeMets boundaries are:

- Efficacy interim analysis (138 events, i.e. 70% expected events): p-value to reject  $H_0 \leq 0.015$  (equivalent to the stopping boundaries Z-Scale:  $\pm 2.437$ )
- Final analysis (197 events, i.e. 100% expected events): p-value to reject  $H_0 \leq 0.045$  (equivalent to the stopping boundaries Z-Scale:  $\pm 2.0$ )

The results of the interim analyses will be given only to the IDMC members.

Safety analysis will be summarized on the Safety Population (i.e. all patients who receive any part of investigational treatment). Incidence of AEs will be summarized by system organ class and preferred term according to MedDRA coding, and will be presented by treatment groups and

overall. AEs will be summarized by grade (NCI CTCAE v5.0), according to the worst grade experienced.

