#### Other secondary endpoints

- Time to worsening in prostate cancer-related urinary symptoms, defined as an increase from baseline of greater or equal to 8 points in the urinary symptom scale/score (PRURI) measured using the prostate cancer module of the European organisation for research and treatment of cancer (EORTC) quality of life questionnaire (QLQ) (EORTC-QLQ-PR25).
- Time to next symptomatic skeletal event, defined as the time from randomisation until first occurrence of one of the following: a symptomatic fracture, radiation or surgery to bone or a spinal cord compression (PCWG3 criteria).

**Note:** *The occurrence of these events will be determined by investigator evaluation. No systematic X-Ray will be performed.*

- Complete PSA response (defined as PSA  $\leq$  0.2 ng/ml) at 6 months.
- Prostate cancer-specific survival, defined as the time from randomisation to the date of death due to prostate cancer (deaths due to other causes will be censored).
- Time to deterioration for EORTC QLQ-PR25 symptom subscales, defined as the first decline in the HRQoL score from baseline equal to or greater than the minimally important difference (MID; a measure of clinical significance) defined as half the standard deviation of the baseline value for each subscale.
- Time to first subsequent systemic anti-cancer therapy (SACT) defined as the time from randomisation to the date of initiation of any SACT for CRPC, following initiation of the study treatment.
- Efficacy of subsequent SACT will be assessed according to rPFS, OS, and PFS after next line of treatment (PFS2); defined as the time from randomisation to second objective disease progression, or death from any cause, whichever first.
- Health related quality of life will be evaluated using the EORTC-QLQ-C30, EORTC-QLQ-PR25 and BPI-SF questionnaires.
- Geriatric status will be evaluated using the Geriatric Core Dataset (G-Code) assessment.
- Impact of sarcopenia on overall survival will be evaluated by comparing the distribution of overall survival between sarcopenic and non-sarcopenic patients.
- Impact of sarcopenia on treatment response will be evaluated by comparing rate of response in sarcopenic and non-sarcopenic patients.

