### 7.3.5. Visit 5 - Day 180 (±7 days)

The following should be performed:

- Complete clinical examination (major body systems).
- Collection of height and body weight.
- Measurement of vital signs (blood pressure, seated heart rate, body temperature).
- Assessment of ECOG performance status.
- Electrocardiogram (only in case of abnormal results at screening visit, or if clinically indicated by patient symptoms)
- Assessment of ongoing toxicities including pre-existing symptoms and any concomitant therapies received.
- Haematology analysis (see Table 3, page 47).
- Serum chemistry (see Table 3, page 47).
- Measurement of serum PSA and testosterone levels.
- **Patients who provide additional informed consent:** Abdominal circumference, body mass index (BMI) and maximum handgrip strength using a hand dynamometer. Handgrip strength should be measured twice.
- Dispensation of treatment for 60 days.

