## 10.2. Trial populations to be analysed

- Intent-to-treat (ITT) population: all randomised participants
- Safety population: participants who took at least one dose of trial treatment/intervention

For primary and secondary efficacy endpoints, the analysis will be performed on the ITT population, i.e. all randomised patients will be included, whether eligible or not, compliant or not. Patients will be analysed according to their randomisation arm, regardless of the actual treatment received.

Safety analyses will be performed on the safety population. Patients will be analysed according to the treatment received, regardless of the arm to which they were randomised.

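### The only missing-data rule for 6-month complete PSA response drops patients without a value, although the protocol says secondary efficacy is analysed on all randomised patients

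*Protocol*

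**What the plan says.** Section 3.2.2 lists among the other secondary endpoints "Complete PSA response (defined as PSA" ≤ "0.2 ng/ml) at 6 months". The definition sets a threshold and a time point. It does not say how to classify a patient with no PSA at that time. The matching visit is Visit 5, Day 180 ±7 days (section 7.3.5), where PSA is measured.

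Section 10.3.6 is the whole missing-data section. Time-to-event endpoints are handled by censoring. For all others, "valid percent (excluding missing values) will be reported in the descriptive tables", and "number of missing data will be reported for each parameter". It does not refer the matter to the SAP, whereas section 10.3.2 does so for secondary censoring rules and section 10.3.4 for the quality-of-life hypotheses.

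Section 10.2 says: "For primary and secondary efficacy endpoints, the analysis will be performed on the ITT population, i.e. all randomised patients will be included". The statistical part of the protocol summary repeats this and adds: "Qualitative data will be expressed as percentages and compared between the treatment groups using the chi-square test (or the Fisher exact test"). Section 10.3.7 treats endpoints other than the primary and key secondary ones as exploratory, each tested at two-sided 0.05 without adjustment.

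**The concern.** A percentage that leaves out patients without a value does not include all randomised patients. Sections 10.2 and 10.3.6 therefore cannot both govern the same binary endpoint. The percentages are also meant to be compared between arms by a chi-square or Fisher test, so the choice of denominator reaches an inferential result.

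Patients who die before Day 180 have no value, and those who withdraw consent have no further required visit. After stopping for radiographic progression, no study-specific evaluation is required beyond the end-of-treatment visit (sections 7.4, 7.5 and 7.5.1), so a Day-180 PSA depends on what is in the medical file. If these patients are mostly non-responders, valid percent overstates the response rate and describes response among those still observed, not among those randomised.

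**Working it through.** **Inputs (section 10.1).** Median rPFS 12 months in control; HR 0.65; drop-out hazard 0.014 in both arms; 150 patients per arm. The unit of the drop-out hazard is not stated. It is read as per month, which the check below supports.

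**Reproducing the design.** Events needed by Schoenfeld's formula: 4(1.960 + 1.036)²/(ln 0.65)² = 194; Freedman's formula gives 200; the protocol states 197. With exponential rPFS, the stated drop-out hazard and the accrual table (uniform entry within each period), month 75 gives 107.8 + 88.9 = 196.7 events and 26.1 + 33.1 = 59.3 drop-outs (sum of unrounded values), or 19.8% of 300. The protocol states 197 events and 19.3%. The inputs are therefore being read as intended.

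**Status at month 6.** With λ the rPFS hazard and d = 0.014, the share with an event or drop-out is 1 − exp[−6(λ + d)], split in the ratio λ : d.
- Control: λ = ln 2/12 = 0.0578; 1 − exp(−6 × 0.0718) = 35.0%, of which 28.2% events and 6.8% drop-outs.
- Experimental: λ = 0.65 × 0.0578 = 0.0375; 1 − exp(−6 × 0.0515) = 26.6%, of which 19.4% events and 7.2% drop-outs.

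**Missingness and inflation.** The protocol does not say how many rPFS events leave no Day-180 PSA, so a fraction f is varied. Missing share m = drop-out share + f × event share. If no missing patient is a responder, valid percent equals the all-randomised rate times 1/(1 − m).

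| f | Missing, control | Missing, experimental | Factor, control | Factor, experimental |
|---|---|---|---|---|
| 0 (drop-out only) | 6.8% | 7.2% | 1.07 | 1.08 |
| 0.25 | 13.9% | 12.1% | 1.16 | 1.14 |
| 0.5 | 20.9% | 16.9% | 1.26 | 1.20 |
| 1 (upper bound) | 35.0% | 26.6% | 1.54 | 1.36 |

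At f = 1 the denominators are about 98 and 110 instead of 150 and 150.

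**Effect on the comparison.** The protocol gives no PSA response rates. Assume 20% v 40% of all randomised (difference 20 points, ratio 2.00).
- f = 0: 21.5% v 43.1%; difference 21.7 points, ratio 2.01.
- f = 0.5: 25.3% v 48.1%; difference 22.9 points, ratio 1.90.
- f = 1: 30.8% v 54.5%; difference 23.7 points, ratio 1.77.

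With 30% v 50% and f = 1, the result is 46.1% v 68.1%: difference 22.0 points, ratio 1.48 instead of 1.67. At f = 1 the difference widens only if the true ratio exceeds 0.538/0.362 = 1.49. So the ratio shrinks whenever more control patients are missing, while the difference can move either way.

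**The case against.** The strongest reply is that 10.3.6 describes how tables are displayed, not how response is estimated. It mentions descriptive tables, requires missing counts (so a reader can rebuild the all-randomised rate) and leaves the ITT sentence in place. Responder classification and visit windows often sit in the SAP. This would carry the day if 10.3.6 were silent. It is not silent: it states a rule for all non-time-to-event endpoints and is the only such rule, and the summary compares the resulting percentages by test. A SAP that followed it would carry the conflict forward.

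Other objections stand and limit the point.
- A reader might infer that everyone who progresses before Day 180 leaves the denominator. The protocol does not support that. PSA is measured at the end-of-treatment visit (section 7.4), PSA levels are collected from the medical file in long-term follow-up (section 7.5), and patients who stop for reasons other than progression or consent withdrawal keep the PSA schedule (section 7.5.1). The first scheduled scan is Day 120, and Appendix 3 asks for new bone lesions to be confirmed at least 6 weeks later. So 35.0% v 26.6% is an upper bound.
- A reader might also infer that the bias is known to differ between arms. With drop-out alone, missingness is 6.8% v 7.2%, practically equal. A gap appears only as rPFS events leave no PSA, and then only because an HR of 0.65 is assumed.
- The inflation factors assume that no missing patient would have responded. This is right by convention for deaths. If drop-out is unrelated to response, valid percent is not biased by it.

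**Conclusion.** The conflict between 10.3.6 and 10.2 is real. For 6-month complete PSA response, the rule as written removes patients who died or withdrew, plus progressors with no PSA on file, and overstates the response rate to the extent that they are non-responders. The factor lies between 1.07 and 1.54 in control and between 1.08 and 1.36 in the experimental arm. That range rests on the protocol's exponential hazards, a monthly reading of the drop-out hazard, f between 0 and 1, and no responders among the missing. The upper end is not a forecast.

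The protocol does not establish an unequal bias between arms; it is a projection under the design alternative. The consequence is modest: the endpoint is exploratory under section 10.3.7 and outside the Hochberg family, so no primary or key secondary conclusion depends on it. It is still worth correcting, because a tested efficacy percentage should have one defined denominator, and the correction is cheap.

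**What to change.** Add to section 10.3.6, and carry into the SAP: for complete PSA response at 6 months, the denominator is all randomised patients; patients with no PSA in the Day-180 window, including deaths and withdrawals, count as non-responders; a PSA observed in the window is used as section 3.2.2 defines it, whatever the progression status. Progressors should not be made non-responders by rule, because that would override an observed qualifying PSA and change the endpoint. Keep valid percent with missing counts as a supportive table.

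The cost is one sentence and one extra table, with no new data or visits. The downside is that reported response rates will be lower than valid percent would show, and a drop-out who would have responded is counted against his arm.

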#### **10.3.7. Analysis Specifications**

In general, all hypotheses testing will be performed at a 2-tailed significance level of  $\alpha = 0.05$ . All interval estimations will be reported using 95% confidence intervals.

The following endpoints are considered as key secondary endpoints:

- Castration-resistant prostate cancer-free survival,
- Clinical progression-free survival,
- Overall survival,

Key secondary efficacy endpoints will be tested using the Hochberg test procedure to control the familywise type I error rate; i.e., testing will begin with p value  $P_{(m)}$  with corresponding hypothesis  $H_{(m)}$ , where  $P_{(m)}$  is the largest ordered p values amongst 'm' secondary endpoints (i.e., "the least significant p-value") and  $H_{(m)}$  is the corresponding hypothesis. If  $P_{(m)} \leq \alpha$ , then all null hypotheses are rejected. If not, then  $P_{(j)}$ , the (j)th largest p-value, is compared with  $\alpha/(m-j+1)$ . If smaller, then all

hypotheses from  $H_{(j)}$  to  $H_{(1)}$  are rejected. The testing procedure continues in this manner until no significant result is found. This procedure controls the overall level of significance at the 2-tailed, 0.05 level.

All other endpoints will be considered as exploratory endpoints and will also be analysed. No adjustment for multiple testing will be made. Each endpoint will be tested at a 2-tailed 0.05 level of significance.

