### 10.1. Statistical hypothesis and sample size determination

The primary evaluation criterion/endpoint for this study is radiographic progression-free survival (Section 3.2.1).

Assuming a median rPFS of 12 months for the control group, a planned sample size of 300 subjects will be required to provide an 85% power to detect at least a HR of 0.65 (median rPFS 12 months in the standard arm versus 18.5 months in the experimental arm) at a 2-tailed significance level of 0.05 and a drop-out hazard rate in both arms of 0.014 (i.e. a maximum 19.3% drop-out rate at the end of study corresponding to non-evaluable or study withdrawal patients).

The number of **randomised patients will be 300 patients** (150 patients per arm). The dropout rate will be monitored during the study and in case of increased drop-out the sample size may be adjusted accordingly.

Based on the randomization rates observed since the inclusion of the first patient and the projected rates according to the opening of investigator sites (see below), patient inclusion-randomisation is expected to be complete in 60 months.

	Number of randomized patients during the period	Cumulative number (cumulative percentage) of randomized patients at the end of the period
March 2022-Feb 2023	18 pts (1.5 pts/months)	18 (6%)
March 2023-Feb 2024	50 pts (4.167 pts/months)	68 (22.67%)
March 2024-Feb 2025	53 pts (4.4 pts/months)	121 (40.33%)
Mars 2025-Feb 2027*	179 pts (7.5 pts per month)*	300 (100%)*

\*Grounded on projections

An additional 15 months following termination of accrual (i.e. a total of 75 months since the randomization of the first patient) is expected to obtain the required 197 events, assuming that events will follow an exponential distribution with a constant hazard rate.

The final analysis is scheduled 10 years after the last patient inclusion-randomisation.

 Based on data from the control arm of the LATITUDE trial (Fizazi, 2017), and taking into account that (i) patients with oligo-metastatic disease (low risk patients) will not be enrolled, and (ii) some patients are expected to die from other causes before they reach a progression endpoint, making the median rPFS probably shorter than that seen in the LATITUDE trial

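### Protocol section 10.3.7 words Hochberg's rule against its own symbols, and its overall 0.05 claim does not cover rPFS plus a key secondary family that is not gated on it

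*Protocol*

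**What the plan says.** Section 10.3.7 of the protocol introduces the family with "The following endpoints are considered as key secondary endpoints" and lists CRPC-free survival, clinical progression-free survival and overall survival, so m = 3. It names the method: "Key secondary efficacy endpoints will be tested using the Hochberg test procedure to control the familywise type I error rate".

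It then describes the steps.
- P(m) "is the largest ordered p values amongst 'm' secondary endpoints". When P(m) does not exceed alpha, every null hypothesis in the family is rejected.
- Failing that, P(j), "the (j)th largest p-value, is compared with" alpha/(m-j+1). A value below that threshold leads to rejection of H(j) and every hypothesis of lower index.
- On when to stop, it says: "The testing procedure continues in this manner until no significant result is found".
- On the error level that results, it claims: "This procedure controls the overall level of significance at the 2-tailed, 0.05 level".

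The protocol summary says only this: "The analysis of the secondary endpoints will be performed using a formal adjustment for multiple testing". Section 10.1 gives rPFS a two-sided 0.05, and section 10.4 spends it over an interim look at 138 events and a final look at 197. The only analysis made conditional on a positive rPFS result is the independent-review sensitivity analysis (sections 6.1.1 and 10.3.2). Section 10.1 also states: "The final analysis is scheduled 10 years after the last patient inclusion-randomisation".

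**The concern.** The paragraph is the decision rule for three claims, one of them overall survival, and its sentences do not agree. Two examples with m = 3 show it.

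- p = 0.30, 0.20, 0.04. By the symbols nothing is rejected, because 0.04 exceeds 0.0167. By the words, with j = 3, the smallest p-value is set against 0.05 and is rejected.
- p = 0.30, 0.20, 0.01. By the symbols the hypothesis with p = 0.01 is rejected. By the stopping sentence, testing ends before 0.01 is examined.

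A pre-specified rule should leave no choice among such readings once the data are known. Separately, the paragraph claims control of the overall level at 0.05, while the primary endpoint has a 0.05 of its own and no stated link joins the two.

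**Working it through.** **Inputs.** m = 3 and alpha = 0.05 two-sided (section 10.3.7); rPFS at 0.05 two-sided, looks at 138 and 197 events (sections 10.1 and 10.4). The protocol gives no correlation between endpoints, so equal correlations of 0 to 0.7 are assumed. Error rates are under the global null, from 2,000,000 simulated draws of normal test statistics, with exact values where the endpoints are independent.

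**1. Thresholds by the symbols.** P(3) is the largest, so P(j) is the j-th smallest:
- j = 3 (largest): 0.05
- j = 2 (middle): 0.05/(3-2+1) = 0.025
- j = 1 (smallest): 0.05/(3-1+1) = 0.0167

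This is Hochberg's rule, and it reproduces the stated 0.05 within the family (row A below).

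**2. Thresholds by the words.** If P(j) is the j-th largest, j = 2 is still the middle p-value at 0.025, but j = 3 is the smallest at 0.05/(3-3+1) = 0.05. Only the last step changes. Any rejection then requires only that the smallest p-value be at most 0.05, so with independence the error is 1 - 0.95^3 = 14.3%.

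**3. Stopping sentence.** If testing ends once the middle p-value fails, a rejection needs P(3) <= 0.05 or P(2) <= 0.025. With independence:
- P(2) <= 0.025: 3(0.025^2)(0.975) + 0.025^3 = 0.00184
- P(3) <= 0.05 with P(2) > 0.025: 0.025^3 + 3(0.025^3) = 0.00006
- total: 0.19%

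If testing ends as soon as the largest fails, the error is 0.05^3 = 0.0125%. Both are far below 5%.

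| Reading | corr. 0 | 0.3 | 0.5 | 0.7 |
|---|---|---|---|---|
| A. Symbols (Hochberg) | 4.9% | 4.8% | 4.5% | 4.1% |
| B. Words: smallest p at 0.05 | 14.2% (exact 14.3%) | 13.6% | 12.6% | 10.9% |
| C. Stop when the middle p fails | 0.2% | 0.5% | 1.0% | 1.6% |
| D. Stop when the largest p fails | 0.01% | 0.09% | 0.3% | 0.9% |
| E. rPFS plus family A, no gate | 9.7% | 9.3% | 8.5% | 7.5% |
| F. rPFS plus family A, gated on rPFS | 5.0% | 5.0% | 5.0% | 5.0% |

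**4. Primary plus family.** A Lan-DeMets O'Brien-Fleming calculation at 138/197 returns Z = 2.437 and 2.000 (nominal 0.0148 and 0.0455). This agrees with section 10.4 and confirms that rPFS uses the whole 0.05. A second, separate 0.05 family gives, with independence, 1 - 0.95 x (1 - 0.0492) = 9.7%, and at most 1 - 0.95^2 = 9.75%. Rows E and F represent rPFS by a single test at 0.05.

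**The case against.** The strongest defence is that the method is named and the notation is right, so any statistician would program correct Hochberg. The 14.3% reading is also incoherent within the paragraph. At j = 1 it would set the largest p-value against alpha/3, although the preceding step sets it against alpha. At j = 3 it would reject all three hypotheses, including the one whose p-value had just exceeded 0.05. It further requires ignoring the stopping sentence, which taken literally would not let the smallest p-value be reached. All of this stands. It makes the threshold error a wording error, and 14.3% the cost of one literal reading, not of the rule the sponsor most likely intends. It does not remove the contradiction.

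On the missing gate, the defence is that a SAP may supply one, and that the 0.05 sentence may mean the key secondary family alone. That is fair as far as silence goes. But the protocol makes a positive statement about the overall level that its own text supports only within the family.

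Two stronger inferences are tempting and not supported. A reader might count the reversed stop as a further source of inflation; rows C and D show that it is conservative. A reader might also infer from the two analyses called final that overall survival will be tested at 5% on two dates. No section says so, and section 10.3.2 ties the 197-event analysis to the primary endpoint only.

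**Conclusion.** Section 10.3.7 contradicts itself and needs correcting, but the Hochberg rule in its symbols is sound and holds 5% within the three-endpoint family (4.9% to 4.1% over the assumed correlations). The word for the rank of P(j) is wrong; followed literally, it raises the familywise error to as much as 14.3% with independence. The stopping sentence is wrong in the other direction and can leave the smallest p-value untested, at a cost in power. The overall 0.05 claim holds at most within the family: with no condition on rPFS, primary plus key secondaries reach about 9.7% if independent and 8.5% at correlation 0.5. These figures assume the global null and equal correlations that the protocol does not give. A reader might conclude that the procedure as such fails to control 5%; the documents do not support that.

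**What to change.** Replace the description with explicit steps. Order P(1) <= P(2) <= P(3).
- If P(3) <= 0.05, reject all three hypotheses.
- Otherwise, if P(2) <= 0.025, reject H(1) and H(2).
- Otherwise, if P(1) <= 0.0167, reject H(1).
- Stop at the first rejection.

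Then choose one of two statements on the overall level:
- Test this family only if rPFS crosses its group-sequential boundary. Error for primary plus family under the global null is then 5.0%. The cost is that the key secondary results are descriptive if rPFS fails.
- Or keep the family ungated and limit the 0.05 statement to the key secondary endpoints. This costs nothing in power but gives up the study-wide claim.

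In section 10.1, give the 10-year analysis a name that distinguishes it from the 197-event final analysis of rPFS. When overall survival is tested is for the sponsor to set; tying it to the rPFS analysis would trade away maturity of the survival data and is not needed to cure this point. The wording correction is one paragraph with no effect on sample size, and should be made before comparative data are seen.
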